10.3 IRECIST

Immunotherapeutics may result in infiltration of immune cells leading to transient increase in the size in malignant lesions, or undetectable lesions becoming detectable. The criteria are identical to those of RECIST 1.1 in many respects but have been adapted to account for instances where an increase in tumour burden, or the appearance of new lesions, does not reflect true tumour progression. Key differences are described below. All responses defined using iRECIST criteria are designated with a prefix. iRECIST time-point and best overall responses will be recorded separately.

Confirming progression

Unlike RECIST 1.1, iRECIST requires the confirmation of progression and uses the terms unconfirmed progression (iUPD) and confirmed progression (iCPD). Confirmatory scans should be performed at least 4 weeks, but no longer than 8 weeks after iUPD.

iCPD is confirmed if further increase in tumour burden, compared to the last assessment, is seen as evidenced by one or more of the following:

- Continued increase in tumour burden (from iUPD) where RECIST 1.1 definitions of progression had been met (from nadir) in target, non-target disease or new lesions
 - Progression in target disease worsens with an increase of at least 5 mm in the absolute value of the sum
 - Continued unequivocal progression in non-target disease with an increase in tumour burden
 - Increase in size of previously identified new lesion(s) (an increase of at least 5 mm in the absolute value of the sum of those considered to be target new lesions) or additional new lesions
- RECIST 1.1 criteria are met in lesions types (target or non-target or new lesions) where progression was not previously identified, including the appearance of additional new lesions.

If iUPD is not confirmed at the next assessment, then the appropriate response will be assigned (iUPD if the criteria are still met, but no worsening, or iSD, iPR or iCR if those criteria are met compared to baseline). The prior documentation of iUPD does not preclude assigning iCR, iPR, or iSD in subsequent time-point assessments or as best overall response (BOR) providing that iCPD is not documented at the next assessment after iUPD.

New lesions

New lesions should be assessed and measured as they appear using RECIST 1.1 criteria (maximum of 5 lesions, no more than 2 per site, at least 10 mm in long axis (or 15 mm in short axis for nodal lesions), and recorded as New Lesions-Target (NLT) and New Lesion-Non-Target (NLNT) to allow clear differentiation from baseline target and non-target lesions. New lesions may either meet the criteria of NLT or NLNT to drive iUPD (or iCPD).

However, the measurements of target lesions should NOT be included in the sum of measures of original target lesions identified at baseline. Rather, these measurements will be collected on a separate table in the case record form.

PD is confirmed in the New Lesion category if the next imaging assessment, conducted at least 4 weeks (but not more than 8 weeks) after iUPD confirms further progression from iUPD with either an increase of at least 5 mm in the absolute value of the sum of NLT OR an

Proprietary confidential information © 2020 Boehringer Ingelheim International GmbH or one or more of its affiliated companies

increase (but not necessarily unequivocal increase) in the size of NLNT lesions OR the appearance of additional new lesions

Table 10.3: 1 Time-point (TP) iResponse

Target Lesions*	Non-Target Lesions*	New Lesions*	Time Point Response	
			No prior iUPD**	Prior iUPD**, ***
iCR	iCR	No	iCR	iCR
iCR	Non-iCR/Non-iUPD	No	iPR	iPR
iPR	Non-iCR/Non-iUPD	No	iPR	iPR
iSD	Non-iCR/Non-iUPD	No	iSD	iSD
iUPD with no change OR decrease from last TP	iUPD with no change OR decrease from last TP	Yes	NA	NLs confirms iCPD if NLs were previously identified and increase in size (≥ 5 mm in SOM for NLT or any increase for NLNT) or number.
iSD	iUPD	No	iUPD	Remains iUPD unless iCPD confirmed based in further increase in size of NT disease (need not meet RECIST 1.1 criteria for unequivocal PD)
iUPD	Non-iCR/Non-iUPD	No	iUPD	Remains iUPD unless iCPD confirmed based on: o further increase in SOM of at least 5 mm, otherwise remains iUPD
iUPD	iUPD	No	iUPD	Remains iUPD unless iCPD confirmed based on further increase in: o previously identified T lesion iUPD SOM ≥ 5 mm and / or o NT lesion iUPD (prior assessment - need not be unequivocal PD)
iUPD	iUPD	Yes	iUPD	Remains iUPD unless iCPD confirmed based on further increase in: o previously identified T lesion iUPD ≥ 5 mm and / or o previously identified NT lesion iUPD (need not be unequivocal) and / or o size or number of new lesions previously identified
Non-iUPD/PD	Non-iUPD/PD	Yes	iUPD	Remains iUPD unless iCPD confirmed based on o increase in size or number of new lesions previously identified

* Using RECIST 1.1 principles. If no PSPD occurs, RECIST 1.1 and iRECIST categories for CR, PR and SD would be the same.

** in any lesion category.

*** previously identified in assessment immediately prior to this TP.

Proprietary confidential information © 2020 Boehringer Ingelheim International GmbH or one or more of its affiliated companies

All patients will have their iBOR from the start of study treatment until the end of treatment classified as outlined below.

Table 10.3: 2 iRECIST Best Overall Response (iBOR)

TPR1	TPR2	TPR3	TPR4	TPR5	iBOR
iCR	iCR	iCR, iPR, iUPD, NE	iUPD	iCPD	iCR
iUPD	iPR, iSD, NE	iCR	iCR	iCR, iPR, iSD, iUPD, NE	iCR
iUPD	iPR	iPR	iPR, iSD, iUPD, NE	iPR, iSD, iUPD, NE, iCPD	iPR
iUPD	iSD, NE	iPR	iPR	iPR, iSD, iUPD, NE	iPR
iUPD	iSD	iSD, iUPD, NE	iSD, iUPD, iCPD, NE	iSD, iUPD, iCPD, NE	iSD
iUPD	iCPD	Anything	Anything	Anything	iCPD
iUPD	iUPD	iCPD	Anything	Anything	iCPD
iUPD	NE	NE	NE	NE	iUPD

- NE = not evaluable that cycle.
- Designation “I” for BOR can be used to indicate prior iUPD to aid in data interpretation.
- For patients with non-target disease only at baseline, only CR or non-CR/non-PD can be assigned at each TPR but is not shown in the table for ease of presentation.

10.4 SPECIFIC COUNTRY ADAPTIONS

Ethical conduct of the study (addendum to [Section 8](#))

This study will be conducted according to the principles of the Declaration of Helsinki (adopted by the 18th World Medical Association (WMA) General Assembly, Helsinki, Finland, June 1964 and last amended by the 64th WMA General Assembly, Fortaleza, Brazil, October 2013) and are consistent with ICH/Good Clinical Practice, and applicable regulatory requirements subject data protection.

Public disclosure and publication policy (addendum to [Section 8](#))

Public disclosure and publication policy will follow Centrale Commissie Mensgebonden Onderzoek (CCMO) requirements and is available on website of CCMO ([R18_3257](#)).

Compensation for injury (addendum to [Section 8](#))

The sponsor/investigator has a liability insurance which is in accordance with article 7, subsection 9 of the WMO.

The sponsor (also) has an insurance which is in accordance with the legal requirements in the Netherlands (Article 7 WMO and the Measure regarding Compulsory Insurance for Clinical Research in Humans of 23th June 2003). This insurance provides cover for damage to research subjects through injury or death caused by the study.

Use and storage of data / body material (addendum to [Section 8.3.3](#))

All coded data will be kept by the sponsor. This link will remain at the trial site for a maximum of 30 years

Plasma samples may be used for further methodological investigations (e.g., stability testing), however only data related to the analyte or bioanalytical assay will be generated by these investigations. The trial samples will be discarded not later than 5 years after the final trial report has been signed (see [Section 5.3.2](#)).

Biobanking for remainders (leftover) from mandatory tumor samples collected for the purposes of the clinical trial, which would otherwise be discarded, can be stored in a biobank for up to 30 years for future research.

Study updates (addendum to [Section 8.6](#))

Start and end date of the study as well as annual progress reports and notification of (early) termination study will be passed on to the Ethics Committee (METc).

11. DESCRIPTION OF GLOBAL AMENDMENT(S)

11.1 GLOBAL AMENDMENT 1

[figure not shown]
Date of amendment	30 Oct 2018
EudraCT number	2017-005046-30
EU number	
BI Trial number	1381-0003
BI Investigational Product(s)	[⁸⁹ Zr]Zr-BI 754111, BI 754091 and BI 754111
Title of protocol	An open label Phase I PET imaging study to investigate the bio-distribution and tumor uptake of [⁸⁹ Zr]Zr-BI 754111 in patients with advanced non-small cell lung cancer and head and neck squamous cell carcinoma treated with BI 754111 in combination with BI 754091
To be implemented only after approval of the IRB / IEC / Competent Authorities	
To be implemented immediately in order to eliminate hazard – IRB / IEC / Competent Authority to be notified of change with request for approval	
Can be implemented without IRB / IEC / Competent Authority approval as changes involve logistical or administrative aspects only	
Section to be changed	
1. Section 1.42. Section 8.13. Section 9.14. Section 10.4
Description of change	
1. Change regarding risk due to radiation burden2. Deletion of wording referring to legal representative and addition of local Ethics Committee reference3. Deletion of obsolete unpublished reference4. New section
Rationale for change	
1. Text adapted to better describe the risk due to radiation exposure and to correctly describe the risk category.2. Ethics committee requirement3. Section to address country specific requirements

11.2 GLOBAL AMENDMENT 2

Date of amendment	27 Jan 2020
EudraCT number	2017-005046-30
EU number	
BI Trial number	1381-0003
BI Investigational Product(s)	[⁸⁹ Zr]Zr-BI 754111, BI 754091 and BI 754111
Title of protocol	An open label Phase I PET imaging study to investigate the bio-distribution and tumor uptake of [⁸⁹ Zr]Zr-BI 754111 in patients with advanced non-small cell lung cancer and head and neck squamous cell carcinoma treated with BI 754111 in combination with BI 754091
To be implemented only after approval of the IRB / IEC / Competent Authorities	
To be implemented immediately in order to eliminate hazard – IRB / IEC / Competent Authority to be notified of change with request for approval	
Can be implemented without IRB / IEC / Competent Authority approval as changes involve logistical or administrative aspects only	
Section to be changed	
1. Flow chart2. Blood sample flow chart3. Section 1.44. [REDACTED]5. Section 3.16. Section 4.2.17. Section 5.18. Section 5.2.39. Section 5.2.6.1.410. Section 5.2.6.2.511. Section 5.4.112. Section 5.4.213. Section 5.6.214. Section 6.215. Section 9.116. Section 10.2 (Appendix)
Description of change	
1. Table and footnotes adapted for considering: a) “administration of pre-treatment medication”,

	
b) optional biopsy at Cycle 1
 
c) changed timepoints for blood sampling,
 
d) changed timepoints for PET imaging
 
2. Table adapted for considering changed timepoints for PK radioactivity sampling, BI754111 PK sampling and PET scan time points in cycles 1 and 23. Update on safety and efficacy information4. [REDACTED]5. Adapted design for part 26. Change in pre-medication information7. Correction8. Additional information in case of criteria for hepatic injury are fulfilled9. Text related to AESI adapted for potential DILI events/hepatic injury and for infusion-related reactions10. Title correction and clarification on exempted events11. Addition of optional biopsy at Cycle 112. Correction13. Adaptation14. Adaptation15. Correction16. Update
Rationale for change	
1. Adaptations for considering:
 
a) Prophylactic treatment to reduce the risk of infusion-related reaction –
 
b) Optional biopsies added to allow for [REDACTED]
 
c) Revised blood sampling time points: To better determine initial clearance, potential non-linearity due to major sink or internalization of [⁸⁹Zr]Zr-BI 754111 to determine if radioactivity concentration in blood correlates well with the image derived input function and the concentration of BI 754111.
 
d) Change in PET scan timepoints has been made to

	
support kinetic based modelling of drug uptake in tumor lesions and organs/ tissues
 
2. See rational c) above3. More recent safety and efficacy information has been added to update the benefit risk section of the protocol. In addition, the risk of infusion related reactions has been described4. [REDACTED]5. Adapted design to consider the additional PET timepoints and the optional biopsy6. Pre-treatment medication has been added to the study prior to administration of the study treatment in order to reduce the risk of infusion related reactions7. To correct erroneous reference8. Language about drug-induced liver injury has been updated to clarify that the Potential DILI Checklist should always be completed when specified liver elevations occur.9. Language about hepatic injury and potential DILI case has been updated to clarify the criteria for liver abnormalities which prompt reporting as AESI and completion of potential DILI checklist. In addition, text has been added for pre-treatment medication prior to administration of the study treatment in order to reduce the risk of infusion related reactions and more detail has been provided on what to do in the event of a Grade 3 or higher infusion related reaction.10. Clarification that hepatic injury does not apply for PD reporting exemption11. Optional biopsy: same rational as above (1, b))12. Text related to cytokines measurement has been deleted as this does not apply in this trial13. Adaptation for considering changed timepoints for PK radioactivity sampling in cycles 1 and 214. Adaptation for considering optional biopsy in C1 and changed timepoints for PK radioactivity sampling in C1 and C215. To correct for actual reference for iRECIST16. To provide more detail on what to do in the event of an infusion related reaction
--	---

APPROVAL / SIGNATURE PAGE

[figure not shown]
[figure not shown]
[figure not shown]
[figure not shown]
[figure not shown]
[figure not shown]
Document Number: c21115267

Technical Version Number: 3.0

Document Name: clinical-trial-protocol-version-03

Title: An open label Phase I PET imaging study to investigate the bio-distribution and tumor uptake of [89Zr]Zr-BI 754111 in patients with advanced non-small cell lung cancer and head and neck squamous cell carcinoma treated with BI 754111 in combination with BI 754091

Signatures (obtained electronically)

Meaning of Signature	Signed by	Date Signed

2. LIST OF ABBREVIATIONS

See Medicine Glossary:

<http://glossary>

Term	Definition / description
AE	Adverse Event
C1	Cycle 1
C2	Cycle 2
CR	Complete Response
CTC	Common Terminology Criteria
CTP	Clinical Trial Protocol
CTR	Clinical Trial Report
DBL	Database Lock
DM&SM	Boehringer Ingelheim Data Management and Statistics Manual
DRA	Drug Regulatory Affairs
DMG	Dictionary Maintenance Group
ECOG	Eastern Cooperative Oncology Group
EMA	European Medicines Agency
FL	Follicular Lymphoma
ICH	International Conference on Harmonisation
iPD	Important Protocol Deviations
LOCF	Last Observation Carried Forward
MedDRA	Medical Dictionary for Regulatory Activities
MQRM	Medical Quality Review Meeting
MTD	Maximum Tolerated Dose
O*C	Oracle Clinical
OR	Objective Response
PD	Progression of Disease
PK	Pharmacokinetics
PR	Partial Response
PSTAT	Project Statistician
PT	Preferred Term
Q1	Lower Quartile

Term	Definition / description
Q3	Upper Quartile
RECIST	Response Evaluation Criteria in Solid Tumours
iRECIST	Immune Response Evaluation Criteria in Solid Tumours
REP	Residual Effect Period
RPM	Report Planning Meeting
SA	Statistical Analysis
SAE	Serious Adverse Event
SD	Stable Disease
StD	Standard Deviation
SMQ	Standardised MedDRA query
SOC	System Organ Class
SUVmean	Average Standard uptake value
SUVpeak	Standard uptake value in a 1ml sphere around highest SUV pixel
TESS	Treatment Emergent Signs and Symptoms
ToC	Table of Contents
TMW	Trial Medical Writer
TS	Treated Set
TSAP	Trial Statistical Analysis Plan

3. INTRODUCTION

As per ICH E9 ([1](#)), the purpose of this document is to provide a more technical and detailed elaboration of the principal features of the analysis described in the protocol, and to include detailed procedures for executing the statistical analysis of the primary and secondary variables and other data.

This Trial Statistical Analysis Plan (TSAP) assumes familiarity with the Clinical Trial Protocol (CTP), including Protocol Amendments. In particular, the TSAP is based on the planned analysis specification as written in CTP Section 7 “Statistical Methods and Determination of Sample Size”. Therefore, TSAP readers may consult the CTP for more background information on the study, e.g., on study objectives, study design and population, treatments, definition of measurements and variables, planning of sample size, and randomization.

In the following, study medication always refers to [⁸⁹Zr]Zr-BI 754111, ezabenlimab (BI 754091) and BI 754111.

SAS® Version 9.4 or a newer version and Phoenix TM WinNonlin ® version 8.1 will be used for PK analyses. SAS® Version 9.4 or newer version will be used for all analyses.

4. CHANGES IN THE PLANNED ANALYSIS OF THE STUDY

This is the initial version of TSAP and there is no change in the analysis plan since the finalization of the protocol version 3.0.

The study was prematurely terminated by the sponsor.

Other than specified in the CTP, the following analyses will not be performed by BI:

[REDACTED]

[REDACTED]

[REDACTED]

5. ENDPOINTS(S)

5.1 PRIMARY ENDPOINT(S)

The main objective of this study is to determine the biodistribution and intra-tumor accumulation of [⁸⁹Zr]Zr-BI 754111 at baseline and its change upon treatment.

The primary endpoint of this study is:

- Standardized uptake values (SUVs) of [⁸⁹Zr]Zr-BI 754111 for tumor uptake at baseline (Cycle1) and post BI 754111 dose (up to Cycle2 Day8).

[figure not shown]
5.2 SECONDARY ENDPOINT(S)

[figure not shown]
5.2.1 Key secondary endpoint(s)

[figure not shown]
Not applicable; there is no secondary endpoint in this study.

5.2.2 Secondary endpoint(s)

Not applicable; there is no secondary endpoint in this study.

6. GENERAL ANALYSIS DEFINITIONS

6.1 TREATMENT(S)

In this Phase I trial treatments are not randomised.

Patients will receive combination treatment of BI 754111 (600 mg) and ezabenlimab (240 mg). Data of study parts 1 and 2 will be reported together, grouped by (cold) blocking dose of BI 754111 (cohorts).

Table 6.1: 1 Definition of analysing treatment periods for safety analysis

Analysing Treatment Period	Start Date	Stop Date
Screening	Date of informed consent	Date/Time of the first administration of trial medication
On-treatment	Date/Time of the first administration of trial treatment	Date of the last administration of trial medication + 30 days (residual effect period)
Follow-up	Date of the last administration of trial treatment + 31 days	Date of the last per protocol visit

Note: a 30-day safety follow-up period is defined for this trial.

For safety analyses, adverse events (AEs) will be classified to one of the following time periods: “Screening”, “On-Treatment” or “Follow-up”. This will be applied for all adverse events. Detailed rule for assigning AEs to these time periods are listed below:

- If the date of informed consent \leq AE onset date $<$ date/time of first administration of [⁸⁹Zr]Zr-BI 754111, ezabenlimab or BI 754111, then the AE is assigned to “Screening”;
- If date/time of first administration of ezabenlimab or BI 754111 \leq AE onset date \leq date of last administration of [⁸⁹Zr]Zr-BI 754111, ezabenlimab or BI 754111 + 30 days, then the AE is assigned to “On-Treatment”;
- If AE onset date $>$ date of last administration of [⁸⁹Zr]Zr-BI 754111, ezabenlimab or BI 754111 + 30 days, then the AE is assigned to “Follow-up”

For the on-treatment period, the nominal trial medication assigned at the beginning of the first treatment cycle (Cycle 3) will be used as label of the analysing treatment. In cases where patients stop treatment before Cycle 3, the actual treatment doses applied in Cycles 1 and 2 will be used as label. Tables for the on-treatment period will contain a “total” column, representing all doses of trial medication combined.

The first treatment cycle starts with the first administration of any trial medication and lasts for 21 days. Treatment cycles generally consist of 21 days.

Adverse Events (AEs) that have onset date during the Screening or Follow-Up periods will be displayed in separate listings from those occurred during the on-treatment period. Listings of AEs will not present a “total” category.

Labels of each analysing treatment period, analysis numbers, the labels used for display in the tables and listings in the CTR, as well as codes, decodes, sort order and labels for each trial medication used in this trial are provided in the technical document “ADS Plan”.

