3.1 OVERALL TRIAL DESIGN AND PLAN

This is a Phase I open label, non-randomized bio-distribution trial to be conducted in one specialized center. The trial is divided in 2 Parts as described below in [Figure 3.1:1](#) and will be conducted in a staggered approach.

Part 1 – Dosimetry and feasibility assessment – up to 5 patients

Part 2 – Assessment of tumor uptake – up to 35 patients

[figure not shown]

Recommended exp. dose is the BI 754111 dose recommended for the expansion phase of trial 1381-0002.

Figure 3.1: 1 Overall design

- **Part 1** is intended to assess the dosimetry of $[^{89}\text{Zr}]\text{Zr-BI 754111}$, to optimize the imaging time window and the feasibility of $[^{89}\text{Zr}]\text{Zr-BI 754111}$ PET to assess tumor distribution and uptake of BI 754111. The BI 754111 dose administered in this Part will be the dose recommended for the expansion phase of trial 1381-0002. The whole body biodistribution of $[^{89}\text{Zr}]\text{Zr-BI 754111}$ will be assessed and optimal tumor uptake parameters will be developed. See [Figure 3.1: 2](#).

Proprietary confidential information © 2020 Boehringer Ingelheim International GmbH or one or more of its affiliated companies

[figure not shown]
PD= Progression of Disease Bx=Tumor Biopsy

Figure 3.1: 2 Part 1: dosimetry and feasibility assessment

- Part 2 will be initiated following a positive SMC decision after review of all available data from Part 1 in order to assess whether a blockade of $[^{89}\text{Zr}]\text{Zr}$ -BI 754111 has been demonstrated. Patients will be tested for tumor LAG-3 expression at screening. During cycle 1, all patients will undergo baseline PET assessments. During cycle 2 (on-treatment PET assessment), at least 2 doses levels of BI 754111 treatment will be explored in patients tested positive for tumor LAG-3 expression. At least 2 patients should be included per dose cohort. See [Figure 3.1: 3](#).

Up to five patients tested negative for LAG-3 expression will be included in Part 2. These patients will not be part of dose exploration but will be offered treatment with BI 754111 at the dose recommended for the expansion phase of trial 1381-0002. Hence, they will not undergo the on-treatment PET/CT assessment procedures.

After cycle 2, all patients will be treated at the recommended dose.

PD= Progression of Disease Bx=tumor biopsy PET/CT post $[^{89}\text{Zr}]\text{Zr}$ -BI 754111: 2 before CTP 3.0, 3 after CTP 3.0

Figure 3.1: 3 Part 2: assessment of tumor uptake

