3.2 DISCUSSION OF TRIAL DESIGN, INCLUDING THE CHOICE OF CONTROL GROUP(S)

Part 1 will assess the feasibility of the methods. The patients included in Part 1 will have a $[^{89}\text{Zr}]\text{Zr-BI 754111}$ infusion for a baseline PET assessment (prior to first BI 754111 treatment) at Cycle1 and another $[^{89}\text{Zr}]\text{Zr-BI 754111}$ infusion for on-treatment PET assessment (following first BI 754111 treatment) at Cycle2. The baseline PET assessment will include a dosimetry to investigate the tracer ($[^{89}\text{Zr}]\text{Zr-BI 754111}$) dose. During the on-treatment PET assessment, the patients will be administered the dose of BI 754111 recommended for the expansion phase of trial 1381-0002. This dose of BI 754111 treatment will be tested first to evaluate whether a blockade of the $[^{89}\text{Zr}]\text{Zr-BI 754111}$ is possible.

It is estimated that up to 5 patients will be included in Part 1.

The data obtained from these patients will be analysed and reviewed on a regular basis by the SMC. During the SMC reviews, the mass dose of $[^{89}\text{Zr}]\text{Zr-BI 754111}$ might be adapted as needed *based on all imaging data available*. Part 2 will commence based on SMC decision after review of all available data from Part 1.

Part 2 will assess the tumor uptake of $[^{89}\text{Zr}]\text{Zr-BI 754111}$. The patients will be prospectively tested for LAG-3 tumor expression.

The patient tested positive for LAG-3 tumor expression will be included in different dose-cohorts, each cohort exploring one dose of BI 754111 treatment during cycle 2. It is planned to explore at least 2 doses of BI 754111 treatment in this study. At least 2 patients with LAG-3 expressing tumor are needed in each dose cohort in order to assess the degree of blockade of $[^{89}\text{Zr}]\text{Zr-BI 754111}$ uptake upon a certain BI 754111 dose.

A cohort of maximum 5 patients tested negative for LAG-3 expression will be included in Part 2. These patients will undergo the baseline PET assessment for $[^{89}\text{Zr}]\text{Zr-BI 754111}$ tumor uptake but they will not be considered for dose exploration and will not proceed for the on-treatment PET assessment.

For each patient in Part 2, *the cold dose BI 754091 necessary to optimize $[^{89}\text{Zr}]\text{Zr-BI 754111}$* , the dose of BI 754111 treatment to be applied at cycle 2 and the imaging timepoints will be confirmed by the SMC with reference to the data available.

Up to 35 patients might need to be included in Part 2.

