In both Parts:

At screening, all patients should provide two core needle tumor biopsies for LAG-3 IHC testing. These two core needle tumor biopsies (or equivalent) are to be taken from a PET-imageable and evaluable lesion prior to first BI 754091 administration

All patients will be administered the anti-PD-1 treatment BI 754091 alone at day 1 of cycle 1. Thereafter, the anti-LAG-3 treatment BI 754111 will be added to BI 754091 at day 1 of cycle 2 and this combination treatment will be administered on the first day of each cycle.

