4.1.2.2 BI 754111

BI 754111 treatment will be administered at doses expected to be therapeutically active based on non-clinical and clinical data.

The first dose to be investigated is the dose recommended for the expansion phase of trial 1381-0002. This dose was selected based on the data obtained in 1381-0002 dose-escalation cohorts, where 3 to 9 patients each received BI 754111 at dose levels of 4, 20, 80, 200, 400 and 600mg in combination with a flat dose of 240mg BI 754091. No DLTs or AESIs were observed in the dose escalation Part and maximum tolerated dose (MTD) was considered not reached.

The first administration of BI 754111 treatment will take place at Cycle2 Day1. In Part 2, various doses cohorts will be investigated sequentially. In each cohort, the dose applied at Cycle2 Day1 will depend on the magnitude of the blockade observed in the previous dose cohort. It is expected to explore at least two different dose levels of BI 754111 in this trial.

From Cycle3 Day1, the dose BI 754111 dose recommended for the expansion phase of trial 1381-0002 will be applied to all patients.

The treatment will be administered via infusion q3w.

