4.1.4 Drug assignment and administration of doses for each patient

The tracer dose (approximately 4mg in 20mL) of [⁸⁹Zr]Zr-BI 754111 will be injected intravenously via a pump in 10 min with flushing (10 mL physiologic saline). The mass dose might be adapted as per SMC decision. The injection will take place at the department of [REDACTED] Each patient will be administered [⁸⁹Zr]Zr-BI 754111 up to 2 times during the trial, once at Cycle1 no later than Day8 and at Cycle2 after the administration of BI 754091/BI 754111 treatment, if applicable (all patients in Part 1 and only patients tested positive for tumor LAG-3 expression in Part 2).

BI 754091 will be administered via intravenous infusion at the dose of 240mg. The first administration of BI 754091 treatment will take place at Cycle1 Day1 for each patient.

BI 754111 will be administered via intravenous infusion at the recommended expansion dose per trial 1381-0002. The first administration of BI 754111 treatment will take place at Cycle2 Day1 for each patient.

In Part 2, patients tested positive for tumor LAG-3 expression will be administered a lower or a higher dose of BI 754111 treatment at Cycle2 only. The dose allocated at these patients in Cycle2 will be confirmed by the SMC.

At Cycle2 and onwards, BI 754091 and BI 754111 treatment will be administered concomitantly.

For the preparation and administration of BI 754091 and BI 754111, please refer to the instruction provided in the ISF.

For each compound, the different timepoints of administration and the different doses are summarized in the table below.

Table 4.1.4: 1 Administration of doses per study part

Treatment Cycle	Study Part	Day	Dose to be administered
Cycle1 Baseline assessment	Part 1 and Part 2	C1 Day1	BI 754091 treatment: 240mg
		No later than day8	[⁸⁹ Zr]Zr-BI 754111: 4mg or adapted mass dose
Cycle2 On-treatment assessment	Part 1	C2 Day1	BI 754091 treatment: 240mg
			BI 754111 treatment: recommended exp. dose
	Part 2	C2 Day1	[⁸⁹ Zr]Zr-BI 754111: 4mg or adapted mass dose
			BI 754091 treatment: 240mg
			BI 754111 treatment: allocated dose per SMC decision
			[⁸⁹ Zr]Zr-BI 754111: 4mg or adapted mass dose
Cycle 3 and further cycles	Part 1 and Part 2	Cx Day1	BI 754091 treatment: 240mg
			BI 754111 treatment: recommended exp. dose

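### The pooled by-dose summary of SUVpeak change is open to confounding by LAG-3 status, because the recommended-dose scans come from Part 1 patients not selected for LAG-3 and the scans at other doses from LAG-3-positive patients only

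*SAP*

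**What the plan says.** **Part 1.** Up to 5 patients enter sequentially. The inclusion criteria (protocol 3.3.2) set no LAG-3 requirement. On dose, protocol 3.1 says: "The BI 754111 dose administered in this Part will be the dose recommended for the expansion phase of trial 1381-0002".

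**Who has the Cycle 2 tracer.** Protocol 4.1.4: "all patients in Part 1 and only patients tested positive for tumor LAG-3 expression in Part 2".

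**Part 2 dose at Cycle 2.** The text of protocol 4.1.4 says "patients tested positive for tumor LAG-3 expression will be administered a lower or a higher dose of BI 754111 treatment at Cycle2 only". Table 4.1.4: 1 in the same section says "BI 754111 treatment: allocated dose per SMC decision". Up to five LAG-3-negative Part 2 patients receive the recommended dose but have the baseline PET only (protocol 3.1, 3.2).

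**Why LAG-3 status matters to the protocol.** In describing Part 2, protocol 3.2 says: "At least 2 patients with LAG-3 expressing tumor are needed in each dose cohort in order to assess the degree of blockade". Protocol 1.3 assumes that tracer uptake is related to LAG-3 expression. Status is to be measured in both Parts: "At screening, all patients should provide two core needle tumor biopsies for LAG-3 IHC testing".

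**Analysis.** SAP 6.1: "Data of study parts 1 and 2 will be reported together, grouped by (cold) blocking dose of BI 754111 (cohorts". SAP 7.4.1 summarises the SUVpeak change by Cycle 2 dose group, and baseline uptake by the same groups. SAP 7.4 removes only patients who are not evaluable. SAP 7.4.2 rules out sensitivity and further exploratory work on the primary endpoint.

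**The concern.** The protocol keeps LAG-3-negative patients out of the blockade assessment in Part 2 but has no matching rule for Part 1. On the text of 4.1.4, dose, Part and LAG-3 selection then move together: the recommended-dose row holds patients not selected for LAG-3, and every other row holds only LAG-3-positive patients. A tumour with little target has little specific uptake to block. A LAG-3-negative patient in the recommended-dose row would therefore be expected to pull its mean change towards zero.

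Someone reading down the by-dose table could then take a difference in patient selection for a difference in dose, or see a flat dose pattern where there is none. This is the only by-dose display of the primary endpoint in the readable part of the SAP.

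**Working it through.** **The plan's own figures.** The sample size is not based on power, so there is no power figure to reproduce. The counts agree: 5 + 35 = 40 (protocol 7.7), and 30 LAG-3-positive + 5 LAG-3-negative = 35 in Part 2 (protocol 1.4).

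**Who can contribute an on-treatment change, on the text of protocol 4.1.4**

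| Group | Cycle 2 dose | On-treatment PET | Selected for LAG-3 |
|---|---|---|---|
| Part 1 (up to 5) | recommended | yes | no |
| Part 2 positive (up to 30) | other than recommended | yes | positive only |
| Part 2 negative (up to 5) | recommended | no | negative only |

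If Table 4.1.4: 1 governs instead, LAG-3-positive Part 2 patients could also receive the recommended dose. That row would then mix selected and unselected patients, and the other rows would stay positive-only.

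**Baseline table.** Part 2 negatives have a baseline scan and receive the recommended dose. Depending on how the evaluability exclusion in SAP 7.4 is read, they could enter the recommended-dose baseline row, giving up to 5 + 5 = 10 patients there. The change row for the same dose would hold at most the 5 from Part 1.

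**Size of the distortion (illustration).** The documents give no LAG-3 prevalence, effect size or SD, so all of the following are assumptions. Let D be the true mean change in positives at the recommended dose, c the change in negatives, and k the number of negatives among 5.

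Mean = [(5 - k)D + kc] / 5. With c = 0:

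| k | D = -40% | D = -60% |
|---|---|---|
| 0 | -40% | -60% |
| 1 | 4 × (-40)/5 = -32% | 4 × (-60)/5 = -48% |
| 2 | 3 × (-40)/5 = -24% | 3 × (-60)/5 = -36% |
| 3 | 2 × (-40)/5 = -16% | 2 × (-60)/5 = -24% |

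For other values of c the distortion is (k/5)(c - D), so it shrinks as c approaches D.

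**How likely is a negative in Part 1?** If a proportion p of patients is positive, P(at least one negative in 5) = 1 - p^5. The expected mean with D = -40% and c = 0 is -40p.

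To see the effect on a comparison, add a positives-only lower-dose cohort of 3 with a true change of -20%. The last two columns give the share of 200,000 simulated trials in which that cohort appears to block more than the recommended dose.

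| p | P(at least 1 negative) | Expected mean | Patient SD 10 points | Patient SD 20 points |
|---|---|---|---|---|
| 0.3 | 0.998 | -12% | 77% | 69% |
| 0.5 | 0.969 | -20% | 50% | 50% |
| 0.7 | 0.832 | -28% | 23% | 31% |
| 0.9 | 0.410 | -36% | 5% | 15% |
| 1.0 | 0 | -40% | under 1% | 9% |

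Hand check at p = 0.7, SD 10: the difference in means is -28 - (-20) = -8. Its variance is 1600 × 0.7 × 0.3/5 + 100/5 + 100/3 = 67.2 + 20 + 33.3 = 120.5, so the SD is 10.98. Then z = 8/10.98 = 0.73, and the probability is about 0.23.

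Restricting the recommended-dose row to positives restores an expected -40% at every p.

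**The case against.** **The mix is unknown.** A reader might infer that the summary is in fact confounded. The documents do not support that. No section gives the LAG-3 status of the Part 1 patients, and if all were positive the problem disappears.

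**The decision to open Part 2.** A reader might infer that a diluted Part 1 mean determines whether Part 2 opens. The documents do not support that either. The decision in protocol 3.1 concerns within-patient change at a single dose, so there is no dose comparison to confound. Under protocol 8.7 the SMC reviews individual as well as aggregated data, with associated biomarkers, and its procedures sit in a separate plan. Weak blockade in Part 1 could mean an absent target, but the SMC would have the IHC result. The later step, in which "the dose applied at Cycle2 Day1 will depend on the magnitude of the blockade observed in the previous dose cohort", does compare cohorts when Part 1 is the comparator; there too the SMC has patient-level data.

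**A two-positive minimum for Part 1.** A reader might carry the minimum in protocol 3.2 over to Part 1. It is stated for the Part 2 dose cohorts, so this would be a new rule. The trial had also been terminated before the SAP was finalised (SAP 4 and history table), so the rule would have nothing to act on.

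**Other planned analyses.** The optional dose model in protocol 7.3.1 is limited to Part 2, where on-treatment scans are positives-only. Everything is descriptive, and no between-dose contrast is specified. Individual data are listed (protocol 7.3). SAP sections are redacted, so a LAG-3 analysis may exist there.

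**The illustration.** A 0% change in negatives is a simplification. SAP 7.4.1 takes the lower of two time-point means, so with variable measurements even an unblocked patient is expected to fall below zero. Protocol 1.3 also warns that a single biopsy can misrepresent a heterogeneous tumour.

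These points limit the concern to how the by-dose table is read, and make its size unknown. They do not supply the missing stratum: the table as specified groups by dose alone, and listings leave the reader to rebuild the split.

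**Conclusion.** The concern holds as a reporting weakness. As written, the recommended-dose row and the other dose rows differ in LAG-3 selection as well as in dose, and the visible SAP does not separate the two. Whether bias is present depends on at least one Part 1 patient being LAG-3-negative, which the documents do not say.

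Under the stated assumptions the recommended-dose mean could move from -40% to between -32% and -16% with one to three negatives among five, and not at all with none. These figures show scale; they do not estimate what happened. With no hypothesis test planned, the consequence is for interpretation and not for error rates. This is a should-fix reporting change.

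**What to change.** **SAP 6.1 and 7.4.1.**
- Show the SUVpeak change per dose, and the baseline-uptake table, split by screening LAG-3 IHC status and by Part.
- Base any reading between doses on LAG-3-positive patients, with LAG-3-negative patients in a separate row.
- State that differences between doses are otherwise unadjusted.
- Say whether LAG-3-negative Part 2 patients belong in the baseline table.

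**Protocol 4.1.4.** The sentence "patients tested positive for tumor LAG-3 expression will be administered a lower or a higher dose of BI 754111 treatment at Cycle2 only" and the table entry "BI 754111 treatment: allocated dose per SMC decision" must be reconciled, so that it is clear whether any LAG-3-positive Part 2 patient could be in the recommended-dose row. Which statement applies is for the sponsor.

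**Cost.** A few sentences and revised table shells. The IHC is already planned in both Parts, so no new data are needed. The drawbacks are smaller rows in an already small trial, and some misclassification where a biopsy does not represent a heterogeneous tumour.
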